## 3. STUDY DESIGN

## 3.1. Adaptive Features and Risk Management of Study Design

The rationale for the following adaptive features is based on taking an iterative, hypothesis-forming approach in this clinical trial. The following categories will be adapted as shown in Table 6.

**Table 6** Adaptive Features and Boundaries

Adaptive study design category	Adaptive Features	Boundaries
Dose level for the SAD cohorts	SAD dose levels may be adjusted based on safety and available PK data reported in the previous cohort(s).	Doses are intended to escalate; however, they may be adjusted to an intermediate (lower) or equivalent dose, based on safety and available PK data reported in the previous cohort(s).  Escalation from one dose level to the next dose level will not be more than 3-fold the previous dose.
Dose level for the MAD cohorts	Doses for the MAD cohorts will be adapted in accordance with safety and available PK data collected in previous cohorts during the SAD or MAD phase.	The first MAD dose must be lower or equal to a dose administered in a SAD cohort for which safety and PK data are available.  Doses are intended to escalate; however, they may be adjusted to an intermediate (lower) or equivalent dose, based on safety and available PK data reported in the previous cohort(s).  Escalation from one dose level to the next dose level will not be more than three-fold the previous dose.  A MAD daily dose level cannot be higher than the highest dose level tested in SAD.
Dose level for the Smoker cohorts	Smoker cohort dose levels will be adapted in accordance with safety and available PK data collected in previous cohorts during the SAD or MAD phase.	The first Smoker dose must be lower or equal to a dose administered in a MAD cohort for which safety and PK data are available.  Doses are intended to escalate; however, they may be adjusted to an intermediate (lower) or equivalent dose, based on safety and available PK data reported in the previous cohort(s).  Escalation from one dose level to the next dose level will not be more than three-fold the previous dose.  A Smoker cohort daily dose level cannot be higher than the highest dose level tested in the MAD phase.
Dosing frequency for the MAD and Smoker cohorts	The dosing frequency may be modified from once daily to twice daily.	The modification from once daily to twice daily administration will not change the total daily dose outlined in this protocol.

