Altasciences Project Number: CNO-P5-319

	 
Part B and Part C:	MAD and Smoker Phase, Day 14:
$C_{\text{max}}$	Maximum observed concentration
$T_{\text{max}}$	Time of maximum observed concentration; if it occurs at more than one time point, $T_{\text{max}}$ is defined as the first time point with this value
$C_{ au}$	Concentration at the end of the dosing interval. Observed concentration, otherwise the predicted concentration value will be calculated as per Phoenix WinNonlin vs built-in rules for interpolation/extrapolation, and subject to the criteria for PK parameters requiring $\lambda_z$ estimation.
$AUC_{\tau}$	Area under the concentration time curve over the dosing interval at steady state calculated from 0 to 24 hours (dosing interval)
AUC 0-T	Area under the concentration time curve from time 0 (dose administration) to the time of last quantifiable concentration $(T_{last})$
$T_{half}$	Terminal elimination half-life, calculated as $ln(2)/\lambda_Z$
Thalf, eff	Effective half-life, calculated as
	$\tau * \ln 2 / \ln(Rac_{(AUC)}/(Rac_{(AUC)}-1))$ , where $\tau$ is 24 hours 
CL/F ss	Apparent total clearance at steady state, calculated as Dose/AUC $_{\tau}$
Vz/F ss	Apparent volume of distribution at steady state, calculated as Dose/ $\lambda_Z$ * AUC $_{\tau}$
C max /D	Dose-normalized C max
AUC τ /D	Dose-normalized AUC τ
AUC 0-T /D	Dose-normalized AUC 0-T
Rac (Cmax)	Accumulation ratio evaluated by comparing Day 14 C max to Day 1 C max
Rac (AUC)	Accumulation ratio evaluated by comparing Day 14 AUC τ to Day 1 AUC 0-24
Part B and Part C:	MAD and Smoker Phase, Various Days:
$C_{trough}$	Observed concentration at the end of the dosing interval
The following PK ponly	parameters will be used for PK calculation and presented in the PK listings
T last	Time of last measurable observed concentration
C last	Observed concentration corresponding to T last
$\lambda_Z$	Apparent elimination rate constant, estimated by linear regression of the terminal linear portion of the log concentration versus time curve
$\lambda_{Z \; \mathrm{Upper}}$	Upper limit on time for values included in the calculation of $\lambda_z$
$\lambda_{Z \; Lower}$	Lower limit on time for values included in the calculation of $\lambda_z$

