3.1.2 Part B - MAD Phase

Screening of participants will occur within approximately 28 days prior to the first scheduled administration of study medication. Screening data will be reviewed to determine subject eligibility. Subjects who meet all inclusion criteria and none of the exclusion criteria and who consent to participation will be admitted to the CRU for baseline evaluations before dosing (Day -1). All baseline safety evaluation results should be available prior to dosing and continued eligibility confirmed.

Subjects will be randomized to SBP-9330 or placebo in 1 of the 3 ascending dose cohorts (10 subjects per cohort in 4:1 [SBP-9330:placebo] ratio) to have a total of 8 subjects receiving SBP-9330 and 2 subjects receiving placebo. An additional MAD cohort (Cohort B4) may be added at the discretion of the Sponsor depending on emerging safety and PK data from previous cohorts.

The proposed MAD design and planned escalation are presented in Table 3.

Table 3: Part B - MAD Phase Design and Dose Levels

Cohort	N (active:placebo)	Dose	Drug administrations
B1	8:2	adaptive	Once daily oral administrations of SBP-9330 or placebo for 14 consecutive days (Days 1 to 14) under fasting conditions
B2	8:2	adaptive	Once daily oral administrations of SBP-9330 or placebo for 14 consecutive days (Days 1 to 14) under fasting conditions
B3	8:2	adaptive	Once daily oral administrations of SBP-9330 or placebo for 14 consecutive days (Days 1 to 14) under fasting conditions
Additional B4	8:2	adaptive	Once daily oral administrations of SBP-9330 or placebo for 14 consecutive days (Days 1 to 14) under fasting conditions

Each subject will receive once daily oral administration of the assigned treatment and dose under fasting conditions (SBP-9330 or placebo) for 14 consecutive days.

The MAD phase of the study may commence in parallel to the SAD or thereafter. The decision on how early the MAD phase of the study may be started and the doses to be administered will be determined by the Sponsor after consultation with the DSMB based on emerging safety and PK data. The first MAD daily dose will be less than or equal to an already well-tolerated SAD dose for which complete safety and PK data are available.

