All relevant safety and available plasma PK data will be reviewed by the DSMB before any dose escalation. The dose levels proposed for MAD cohorts may be adjusted during the course of the study based on preliminary safety and PK data. The dosing frequency may also be changed from once daily to twice daily, without changing the total daily dose outlined in the protocol.

The MAD phase will have a maximum of 4 cohorts. The number of cohorts may be changed at the discretion of the Sponsor depending on the emerging safety and PK data from the previous cohorts. The increase from one dose level to the next dose level will not be more than 3-fold. A MAD daily dose level cannot be higher than the highest dose level tested in SAD.

Subjects will be confined to the CRU from at least 10 hours prior to drug administration until approximately 48 hours after last study drug administration. Subjects will therefore be confined for 17 days and 16 nights (Day -1 to Day 16).

Subjects will return for a follow-up visit approximately 5 days after the last PK blood sample/discharge (Day 21±1).

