T_{\max}	Time of maximum observed concentration; if it occurs at more than one time point, T_{\max} is defined as the first time point with this value
C_{τ}	Concentration at the end of the dosing interval. Observed concentration, otherwise the predicted concentration value will be calculated as per Phoenix® WinNonlin®'s built-in rules for interpolation/extrapolation, and subject to the criteria for PK parameters requiring λ_z estimation.
AUC_{τ}	Area under the concentration time curve over the dosing interval at steady state,

	calculated from 0 to 24 hours (dosing interval)
AUC _{0-T}	Area under the concentration time curve from time 0 (dose administration) to the time of last quantifiable concentration (T _{last})
T _{half}	Terminal elimination half-life, calculated as $\ln(2)/\lambda_Z$
T _{half, eff}	Effective half-life, calculated as $\tau * \ln2 / \ln(Rac_{(AUC)} / (Rac_{(AUC)} - 1))$, where τ is 24 hours ¹
CL/F _{ss}	Apparent total clearance at steady state, calculated as Dose/AUC _τ
Vz/F _{ss}	Apparent volume of distribution at steady state, calculated as Dose/ $\lambda_Z * AUC_{\tau}$
C _{max} /D	Dose-normalized C _{max}
AUC _τ /D	Dose-normalized AUC _τ
AUC _{0-T} /D	Dose-normalized AUC _{0-T}
Rac _(C_{max})	Accumulation ratio evaluated by comparing Day 14 C _{max} to Day 1 C _{max}
Rac _(AUC)	Accumulation ratio evaluated by comparing Day 14 AUC _τ to Day 1 AUC ₀₋₂₄

Parts B and C: MAD nonsmoker and smokerPhases, Various Days:

C _{trough}	Observed concentration at the end of the dosing interval (predose concentrations on Days 2, 7, 11, 12, 13, and 14)
---------------------	--

The following PK parameters will be used for PK calculation and presented in the PK listings only

T _{last}	Time of last measurable observed concentration
C _{last}	Observed concentration corresponding to T _{last}
λ_Z	Apparent elimination rate constant, estimated by linear regression of the terminal linear portion of the log concentration versus time curve
λ_Z Upper	Upper limit on time for values included in the calculation of λ_Z
λ_Z Lower	Lower limit on time for values included in the calculation of λ_Z
Number of Points	Number of data points in computing λ_Z
R ²	Goodness of fit for the terminal phase
Residual area	Extrapolated area (i.e., percentage of AUC _{0-∞} due to extrapolation from T _{last} to infinity: [AUC _{0-∞} - AUC _{0-T}] / AUC _{0-∞} * 100)

¹Sources: Gidal et al., 2017 and Boxenbaum et al., 1995

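### The permitted switch to twice-daily dosing is not matched by the PK definitions: τ stays at 24 h, so effective half-life would be overstated, AUCτ mislabelled and the dose in CL/Fss left ambiguous

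*SAP*

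**What the plan says.** The planned regimen in Parts B and C is once daily for 14 days; SAP 3.1.2 states "Each subject will receive once daily oral administration of the assigned treatment and dose under fasting conditions".

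The same SAP section then allows a different regimen: "The dosing frequency may also be changed from once daily to twice daily, without changing the total daily dose outlined in the protocol". Protocol Table 6 (section 3.1), in a row covering both the MAD and the Smoker cohorts, says "The dosing frequency may be modified from once daily to twice daily", with the boundary that "The modification from once daily to twice daily administration will not change the total daily dose outlined in this protocol". Protocol 3.1 lets adaptations inside the Table 6 boundaries go ahead without prior IRB or regulatory approval.

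The Day 14 parameter definitions are written for once-daily dosing only:

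- AUCτ is "calculated from 0 to 24 hours (dosing interval") in SAP Table 7 and "steady state calculated from 0 to 24 hours (dosing interval") in Protocol Table 15.
- Effective half-life is τ·ln2 / ln(Rac/(Rac−1)), "where τ is 24 hours".
- For Rac(AUC), SAP Table 7 has "Accumulation ratio evaluated by comparing Day 14 AUC", that is AUCτ, set against Day 1 AUC0–24.
- CL/Fss is Dose divided by AUCτ, and Vz/Fss uses the same two terms. Neither table says whether Dose is one administration or the daily total.

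SAP section 11 plans no changes to the protocol-specified analyses. Nothing in either document alters these definitions for a twice-daily cohort.

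**The concern.** A dosing interval of 24 h and a twice-daily regimen cannot both hold. The effective half-life formula is valid only when the accumulation ratio and τ refer to the same single interval. With a dose every 12 h, the 0–24 h window holds two doses on Day 1 as well as on Day 14, so the ratio no longer has the form that the formula inverts. Cτ is defined generically as the concentration at the end of the dosing interval, so in such a cohort Cτ and AUCτ would refer to different intervals.

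Effective half-life, AUCτ, CL/Fss, Vz/Fss and the accumulation ratios are listed among the secondary PK endpoints (SAP Table 1). Two cohorts with identical kinetics would report different effective half-lives only because their dosing frequency differed. The switch is also foreseeable: Protocol 3.5 allows escalation to continue with a divided dose when findings are thought to be related to Cmax. If the problem were noticed only after database lock or unblinding, SAP section 9 would class a corrected calculation as post hoc.

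**Working it through.** **Inputs.** From the documents: τ = 24 h, the effective half-life formula, Rac(AUC) = Day 14 AUCτ / Day 1 AUC0–24, and an unchanged total daily dose after a switch. Assumed: equal doses 12 h apart, linear one-compartment kinetics, fast (near-bolus) absorption, steady state by Day 14, both doses given on Days 1 and 14, and complete AUCs. The human half-life is not given (Protocol 1.2.3 reports no clinical experience), so a range of 4 to 24 h is used.

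**Reproducing the plan under once-daily dosing.** Here τ = 24/1 = 24 h. Let k = ln2/T½ and x = e^(−12k). Then Rac = 1/(1−x²). For T½ = 12 h, x = 0.5, Rac = 1/0.75 = 1.333 and Rac/(Rac−1) = 4, so effective half-life = 24·ln2/ln4 = 12.0 h, the true value. Simulation over 14 days gave the same agreement for half-lives of 4 to 24 h, and Dose/AUCτ returned the true CL/F (ratio 1.000).

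**The same formulas under 12-hourly dosing.** Let A be the total AUC of one administration.

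- Day 1 AUC0–24 = A(1−x²) + A(1−x) = A(2−x−x²)
- Day 14 AUC0–24 = 2A
- Rac = 2/(2−x−x²), so Rac/(Rac−1) = 2/(x+x²)
- Effective half-life by the stated formula = 24·ln2 / ln[2/(x+x²)]

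The correct argument of the logarithm would be 1/x². Because x < 1, (x+x²)/2 exceeds x², so the result is always too long under these assumptions.

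| True T½ (h) | x | Rac, 0–24 h | Stated effective half-life (h) | Error |
|---|---|---|---|---|
| 4 | 0.125 | 1.076 | 6.27 | +57% |
| 6 | 0.250 | 1.185 | 8.96 | +49% |
| 8 | 0.354 | 1.315 | 11.63 | +45% |
| 12 | 0.500 | 1.600 | 16.96 | +41% |
| 24 | 0.707 | 2.522 | 32.95 | +37% |

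With slower absorption (ka = 1/h) the simulated error was +46% to +69% over the same half-lives. A small part of that is the absorption bias already present once daily (12.54 h for a true 12 h).

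**AUCτ and CL/Fss.** With total daily dose D, Day 14 AUC0–24 = D/(CL/F), the same as once daily (ratio 1.000) and 2.00 times AUC0–12. So D/AUC0–24 gives CL/F exactly, while (D/2)/AUC0–24 gives 0.500 of it. The dose and AUC terms of Vz/Fss behave in the same way.

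**Two conditions that change the picture.**

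- *Day 14 dosing.* If only the morning dose were given on Day 14, Rac falls below 1 for half-lives of 4 to 8 h and the formula has no value; at 12 h with fast absorption it returns 9.29 h, too short.
- *Sampling.* The listed Day 14 schedule has no sample between 12 and 24 h. With both doses given, observed AUC0–24 would be 64% to 93% of the true value, and CL/Fss with the daily dose 1.08 to 1.57 times the true value.

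**Check of the fix.** With τ = 12 h throughout and T½ = 12 h: Rac(0–12) = 1/(1−x) = 2.00, effective half-life = 12·ln2/ln2 = 12.0 h, and (D/2)/AUC0–12 gives CL/F (ratio 1.000).

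**The case against.** The case for leaving the text alone is that all planned MAD and Smoker cohorts are once daily and the formulas are correct for them. The 24 h can be read as the value of the dosing interval under the planned regimen rather than as a rule for every regimen. The SAP could still be updated before lock or unblinding if a switch occurred, since the waiver of prior approval in Protocol 3.1 does not prevent that. The parameters are descriptive and secondary.

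Much of this stands: the problem is conditional and does not touch the primary safety endpoints. It does not dispose of the point, because τ is set to 24 h in the half-life formula without qualification, the switch is a pre-specified option, and no text connects the two.

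A reader might infer more than the documents support:

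- *That CL/Fss would simply be wrong.* It is exact if Dose means the total daily dose over a fully sampled 0–24 h. The defect is that Dose is undefined.
- *That AUCτ would be numerically wrong or not comparable with once-daily cohorts.* The 0–24 h value is a valid daily exposure and, at equal daily dose under linear kinetics, equals the once-daily value; only its label as one interval fails. Likewise, Rac over 0–24 h is a legitimate ratio of daily exposures and misleads only inside the half-life formula.
- *That effective half-life would be doubled.* That needs a 12 h ratio combined with τ = 24 h, and the plan pairs 24 h AUCs with τ = 24 h.

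**Conclusion.** The point holds as a conditional inconsistency present in both documents. If a cohort is switched to twice-daily dosing and both Day 14 doses are given, the stated effective half-life is biased upward, by about 37% to 57% for true half-lives of 24 down to 4 h with fast absorption. The direction follows from the algebra; the size depends on the assumed half-life, absorption and one-compartment model. AUCτ would be mislabelled, and CL/Fss and Vz/Fss would depend on an unstated choice of dose, with a factor of two between the readings. Once-daily results are unaffected. The change is worth making before any switch, because the option is already open and the correction is small.

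**What to change.** Make the same edits in SAP Table 7 and Protocol Table 15, so that the documents do not diverge while SAP section 11 says no changes are planned:

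1. Define τ as the cohort's actual dosing interval, and use that τ in the effective half-life.
2. Compute AUCτ, and the Rac(AUC) that feeds effective half-life, over 0–τ on both Day 1 and Day 14.
3. State that the dose in CL/Fss and Vz/Fss is the dose belonging to the AUC interval used.
4. Keep AUC0–24 as a separate Day 1 and Day 14 parameter, for comparison across regimens and for the exposure stopping criterion in Protocol 3.5.2, which is expressed as AUC over 0–24 h.
5. State that PK sampling in any twice-daily cohort must cover 12–24 h if AUC0–24 is reported. Protocol Table 6 already lets MAD sampling times change, and footnote 1 of Protocol Table 3 gives similar room in the Smoker phase.

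The documents should also record whether a second dose falls on Day 14 in such a cohort, since the calculations depend on it; that choice belongs to the protocol team.

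The cost is a few words in two tables and, only in a twice-daily cohort, some added samples. The listed schedule already covers 0–12 h on both days, so the interval-based parameters need no new samples. Once-daily analyses do not change.

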7.5 Pharmacokinetic Statistical Methodology

All tables, figures and listings (TFLs), when appropriate, will be stratified by cohort and study day; for the food-effect cohort, additional stratification by meal condition will be performed.

7.5.1 Summary Statistics

Summary statistics of the individual concentration data and derived parameters will be calculated with Phoenix[®] WinNonlin[®] for the PK population. Summary statistics will be calculated for concentration at each individual time point and for all PK parameters.

Concentration data will be summarized by group using the following statistics: number of observations (N), arithmetic mean (mean), standard deviation (SD), minimum (min), median, maximum (max), and coefficient of variation (CV%). PK parameters will be summarized using these same statistics, as well as geometric mean and geometric mean CV%.

7.5.2 Statistical Analysis

Dose Proportionality

For all study parts, appropriate dose-normalized PK parameters (C_{\max} and appropriate AUCs) will be assessed graphically for dose-proportionality (with Phoenix® WinNonlin®).

Natural log-transformed PK parameters (C_{\max} and appropriate AUCs) will be assessed statistically for proportionality using SAS. Proportionality analysis will be done using a power model. The power model is defined as:

$$\ln(\text{PK parameter}) = \alpha + \beta \cdot \ln(\text{Dose}) + \varepsilon$$

where α is the intercept, β is the slope and ε is the error term. A linear model with ln-transformed dose as a continuous effect will be fitted. A point estimate and a 90% confidence interval will be derived for the slope (β).

Dose proportionality may be assessed within different dose ranges if deemed appropriate with at least three doses.

Food-Effect Assessment

A statistical comparison will be performed in subjects enrolled in Cohort A3 to evaluate the effect of food on the PK of SBP-9330 with the natural logarithmic transformation of C_{\max} , AUC_{0-T} , and $AUC_{0-\infty}$.

C_{\max} , AUC_{0-T} , and $AUC_{0-\infty}$ will be statistically analyzed using an Analysis of Variance (ANOVA) model. The fixed factors included in this model will be the Fed or Fasting condition, the period at which it was given (Day 1 or Day 8 [or Day 15]), as well as the sequence in which the treatment is under Fed or Fasting condition. A random factor is also added for the subject effect (nested within sequence).

The 90% confidence interval for the exponential of the difference in least-squares (LS) means between the Fed and Fasting conditions will be calculated (Fed to Fasting ratio of geometric LS means).

The formula to estimate the intra-subject coefficient of variation will be: $\sqrt{e^{MSE} - 1}$, where MSE is the Mean Square Error obtained from the ANOVA model of the ln-transformed parameters.

The parameter T_{\max} will be evaluated descriptively.

Steady State

C_{trough} will be displayed graphically and summarized descriptively by day to assess for steady state.

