Abbreviations: CNS = central nervous system; hERG = human ether-à-go-go-related gene; GLP = good laboratory practice; NOAEL = no-observed-adverse-effect level

The high doses for the pivotal (GLP) repeat-dose rat and dog toxicity studies were chosen based on the maximum tolerated dose defined in the dose range-finding studies. At the highest dose in the pivotal (GLP) repeat-dose studies, toxicity was characterized by poor tolerability without specific organ toxicity. In the 14-day pivotal (GLP) toxicity study in rats, doses up to 600 mg/kg/day were well tolerated. Treatment-related findings were limited to minor clinical pathology alterations in glucose, albumin, total protein, A/G ratio, triglycerides and cholesterol (total and HDL), and liver, adrenal gland and spleen weight increases without histopathologic correlates. Based on these findings, the NOAEL of SBP-9330 in rats was determined to be 600 mg/kg/day. At 600 mg/kg/day, the systemic exposure (AUC) values on study day 14 were 635,000 and 2,240,000 hr.ng/mL for males and females, respectively.

In the SBP-9330-nicotine combination study, Wistar rats were administered different combinations of SBP-9330 vehicle or SBP-9330 at 60, 120, 300, and 600 mg/kg/day, followed by a subcutaneous injection of nicotine vehicle or nicotine at 0.3 mg/kg/day. No interactions between SBP-9330 and nicotine were observed in the toxicity or exposure of either SBP-9330 or nicotine. The toxicity of SBP-9330 in this combination study was similar to that observed in the 14-day definitive rat toxicity study with SBP-9330. The findings in this combination study included non-adverse increases in the mean liver to body weight ratios, minimal diffuse hepatocellular hypertrophy, increases in albumin, albumin to globulin ratios, cholesterol,

Altasciences Project Number: CNO-P5-319

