creatinine, glucose and HDL and decreased LDL following treatment. The clinical chemistry findings were within historical control values and were completely reversible following the 4-week recovery period; the liver weight changes were also reversible and the liver findings were considered non-adverse adaptive changes without correlative changes in markers of liver injury (ALT, AST, GGT). SBP-9330 dosed orally at 600 mg/kg/day with a nicotine injection on Day 14 showed Cmax and AUClast for the males at 63,500 ng/mL and 904,000 hr\*ng/mL, respectively, and for the females at 198,000 ng/mL and 2,210,000 hr\*ng/mL, respectively. Nicotine administered subcutaneously at 0.3 mg/kg/day with SBP-9330 (Group 7) on Day 14 showed Cmax and AUClast for the males at 68.1 ng/mL and 94.3 hr\*ng/mL, respectively, and for the females at 73.9 ng/mL and 109 hr\*ng/mL, respectively.

In the 14-day pivotal (GLP) toxicity study in dogs, doses of > 600 mg/kg/day were not tolerated. At > 600 mg/kg/day, treatment-related findings included salivation, vomiting, diarrhea, lethargy, and body weight loss. At this dose, the alterations in clinical pathology, relative organ weight changes and the histopathologic observation limited to lymphoid depletion in the thymus were considered secondary in nature to a general stress-related response due to the poor tolerability at > 600 mg/kg/day. At 200 mg/kg/day, SBP-9330 was generally well tolerated with treatment-related findings limited to occasional episodes of salivation and vomiting. Based on these findings, the NOAEL in dogs was determined to be 200 mg/kg/day. At 200 mg/kg/day, the systemic exposure (AUC) on study day 14 was 382,000 and 430,000 hr.ng/mL for males and females, respectively.

In the *in vitro* genetic toxicity assays, SBP-9330 was negative for mutagenic and genotoxic potential up to the highest testable concentration under the test conditions of the assays. Moreover, SBP-9330 at doses up to 300 mg/kg/day for 12 weeks in male Wistar rats was well-tolerated with no evidence of testicular toxicity based on an evaluation of sperm parameters and histopathological evaluation of the testis/secondary sex organs.

Lastly, SBP-9330 showed low potency to functionally inhibit the cardiac ion channel ether-a-go-go (hERG) with an IC $_{50}$  of 51  $\mu$ M. SBP-9330 had no adverse effects on the nervous system of conscious rats or on cardiovascular and respiratory functions in conscious dogs.

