#### 4. SUBJECT POPULATION

Subjects meeting all the inclusion criteria and none of the exclusion criteria at Screening may be eligible for participation in this study. Continued eligibility will be assessed upon admission to the CRU, prior to the first study drug administration.

Screen failures are defined as participants who consent to participate in the clinical trial but are not subsequently randomly assigned to the study intervention or entered in the study.

An effort will be made to include similar proportions of males and females in the study.

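### The dose-proportionality model omits sex; prespecifying a sex-adjusted power model beside it would protect precision and guard against a chance sex trend across cohorts, at almost no cost

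*SAP*

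**What the plan says.** SAP 7.5.2 (Dose Proportionality) and protocol 8.4.7.2 specify the same power model, with an intercept, a slope on log dose and an error term. "A linear model with ln-transformed dose as a continuous effect will be fitted", and "A point estimate and a 90% confidence interval will be derived for the slope". Neither document sets an acceptance range for that interval. SAP 7.5 stratifies PK outputs by cohort, study day and, for the food-effect cohort, meal condition. Sex appears only among the baseline characteristics in SAP Section 6.

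On sex mix, protocol Section 4 says: "An effort will be made to include similar proportions of males and females in the study". Randomisation (SAP 3.5) allocates active or placebo within each cohort and is not stratified by sex.

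Protocol 1.2.2 gives animal exposure by sex:
- GLP rat study at the NOAEL: "the systemic exposure (AUC) values on study day 14 were 635,000 and 2,240,000 hr.ng/mL for males and females, respectively".
- Rat nicotine-combination study, Cmax and AUC: "for the males at 63,500 ng/mL and 904,000" and "for the females at 198,000 ng/mL and 2,210,000".
- GLP dog study at the NOAEL: "the systemic exposure (AUC) on study day 14 was 382,000 and 430,000 hr.ng/mL for males and females, respectively".

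Protocol 1.2.3 confirms that there is no clinical experience.

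**The concern.** Subjects are randomised to active or placebo, not to dose. The slope is therefore a comparison between cohorts recruited one after another, and the sex mix at each dose depends on who enrols. The recruitment clause concerns the study as a whole and binds no single cohort or active arm.

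If human exposure differs by sex, leaving sex out has two effects. The sex difference goes into the residual and widens the interval for the slope. And if the female share of the one realised trial happens to trend with dose, part of the sex difference is read as a dose effect. Two animal species disagree on whether to expect a sex difference, and the plan has no analysis that would answer the question in humans.

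**Working it through.** The plan states no precision for the slope (SAP 3.2 says the sample size was not set on statistical grounds), so there is no figure to reproduce.

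**Inputs from the documents.** Part A: 150, 300, 600, 1200 and 2400 mg, 6 active subjects each (SAP Table 2). Part B: 3 planned cohorts with 8 active subjects each and adaptive doses (SAP Table 3). Animal exposures: protocol 1.2.2.

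**Assumptions not in the documents.** Within-sex CV 40%, with 30% and 50% as a range; sex 50:50 at random; Part B doses doubling; true slope 1; human female/male ratio R between 1.13 and 3.53.

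**Step 1: ratios.**
- GLP rat AUC: 2,240,000/635,000 = 3.53.
- Rat combination study: AUC 2,210,000/904,000 = 2.44; Cmax 198,000/63,500 = 3.12.
- GLP dog AUC: 430,000/382,000 = 1.13.

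**Step 2: dose information, Part A.** Doses are spaced by ln 2, so Sxx = 6 × (ln 2)² × (4+1+0+1+4) = 28.8 and √Sxx = 5.37.

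**Step 3: interval width under a random mix.** The within-sex variance is ln(1 + 0.40²) = 0.148. Omitting sex adds (ln R)²/4, which is 0.120 at R = 2 and 0.398 at R = 3.53. The half-width is about t(28 df) × SD/√Sxx:
- R = 2: 1.701 × √0.268/5.37 = 0.164.
- R = 3.53: 1.701 × √0.546/5.37 = 0.234.

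Simulated mean 90% half-widths agree:

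| Part, CV | R | Dose only | With sex |
|---|---|---|---|
| A, 40% | 2 | 0.163 | 0.123 |
| A, 40% | 2.44 | 0.186 | 0.123 |
| A, 40% | 3.53 | 0.233 | 0.124 |
| B, 40% | 2 | 0.319 | 0.242 |
| A, 30% | 1.13 | 0.094 | 0.094 |
| A, 50% | 1.13 | 0.149 | 0.151 |

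With no sex effect at all, the extra term widens the interval by about 2 to 3%.

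**Step 4: validity under a random mix.** At CVs of 30% and 50%, the dose-only slope averages 1.00 and its 90% CI covers 89.6 to 90.3% in every scenario with a random mix.

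**Step 5: one realised trend.** Take 2, 2, 3, 4 and 4 females out of 6 across A1 to A5. The shift in slope is ln R × Σn(x − x̄)(p − p̄)/Sxx, where x is log dose and p the female share. The sum is 6 × 0.693 × (2/6 + 1/6 + 0 + 1/6 + 2/6) = 4.16, and 4.16/28.8 = 0.144.
- R = 1.13: 0.144 × 0.122 = +0.02.
- R = 2: 0.144 × 0.693 = +0.10.
- R = 3.53: 0.144 × 1.261 = +0.18.

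Given this trend and a CV of 30%, coverage of the dose-only interval is 74% at R = 3.53 and 89% at R = 1.13.

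**Step 6: how large chance shifts are.** Under a random mix the SD of the shift in Part A is ln R × 0.5/√Sxx. That is 1.261 × 0.5/5.37 = 0.117 at R = 3.53, and 0.011 at R = 1.13. A shift beyond 0.10 in either direction has probability 37% at 3.53, 24–25% at 2.44 and 0% at 1.13. Forcing an exact 50:50 total over all dose groups leaves the SD at 0.119 for R = 3.53, so an overall balance does not help.

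**The case against.** The strongest reply is that the dose-only power model is a recognised choice on which protocol and SAP agree, that dose proportionality is not itself a stated objective or endpoint, and that a human sex effect is only an assumption. All of that stands. The two GLP species disagree, and at the dog ratio adjustment brings nothing. Sex is also only one candidate covariate; body weight is another. These points argue for keeping the dose-only model and adding the adjusted one beside it.

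Three stronger readings are tempting, and the documents do not support them.
- A reader might infer that chance sex imbalance makes the 90% CI invalid or raises the error rate. It does not: over random mixes the sex variance sits in the residual and coverage stays near 90%. With no acceptance range, there is also no formal conclusion to overturn.
- A reader might infer that the slope steers doses in Parts B and C. SAP Section 10 bases the interim PK on Sections 7.1 to 7.4 and lists concentrations, profiles and key parameters. The power model is in 7.5.2, outside that scope.
- A reader might take the 3.5-fold rat difference as the expected human effect. Nothing in the documents establishes that.

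By-sex summary tables would also be weak. With a random mix, a cohort of 6 splits 5:1 or worse with probability 14/64 = 22%, so 1 − 0.78⁵, about 71%, of five-cohort trials would have at least one sex cell with no more than one subject.

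Some mitigation exists: an imbalance would be visible in the baseline tables, and SAP Section 9 allows labelled post hoc analyses. But that label is the reason to act now, because an adjusted slope produced after lock or unblinding would count as post hoc and exploratory.

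**Conclusion.** The point holds as a gap in prespecification, not as a defect in the planned interval. The cost of omitting sex is precision, plus exposure to whatever sex trend the one realised trial happens to have. At a CV of 40% in Part A, the dose-only interval is about a third wider than the adjusted one if the human ratio is 2 (0.163/0.123 = 1.33) and nearly twice as wide at 3.53 (0.233/0.124 = 1.88). At the dog ratio of 1.13 the difference is negligible.

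That the model omits sex, and that no cohort-level rule controls the sex mix, is certain from the text. The size rests on an assumed CV, an assumed human sex ratio and, for Part B, assumed dose spacing.

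**What to change.** In SAP 7.5.2, add a prespecified sex-adjusted power model beside the dose-only one:

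ln(PK parameter) = α + β·ln(Dose) + γ·sex + ε

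Report β from both models with 90% CIs, and exp(γ) as the female/male geometric mean ratio with its 90% CI. Mark sex by symbol on the dose-normalised plots that are already planned, in place of by-sex tables per cohort. Record the addition in SAP Section 11, which now states that no changes from the protocol analyses are planned.

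No new data are needed. The cost is a few lines of SAP text, one extra fit per parameter and one degree of freedom, with a CI about 2 to 3% wider for the adjusted slope if there is no sex effect. The dose-only result remains available unchanged.
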